4.3 Measures Taken to Minimize/Avoid Bias

4.3.1 Subject Numbering

Within each study site, subjects in the study will receive a consecutive subject number. Subject numbers are generated beginning with the study center number (3 digits, assigned by the sponsor) followed consecutively with a unique number for each subject (4 digits, including leading zeros). For example, if the investigator's center number is 301, subject number will be 3010001, 3010002, 3010003, etc., in consecutive order. Subject numbers, once assigned, will not be reused at any center.

4.3.2 Randomization

Subjects will be randomized 1:1 to receive either combination treatment with Liquid Alpha₁-PI (Human) plus SMT or placebo plus SMT.

4.3.3 Blinding

The unblinded study pharmacist or designee, will be the only unblinded study person at each site. Preparation and pooling of study drug (Liquid Alpha₁-PI (Human) and placebo) will be the responsibility of the local unblinded pharmacist or designee. The placebo is sterile 0.9% sodium chloride injection, United States Pharmacopeia (0.9% NaCl, USP) or equivalent. The same total volume of placebo will be prepared so that there are no differences in infusion volume.

Since this is a double-blind, placebo-controlled study, measures will be taken to assure that the placebo infusion will be indistinguishable in terms of commensurate volume from Liquid Alpha₁-PI (Human) infusion volume to that required for the appropriate weight-based dose of Liquid Alpha₁-PI (Human) to maintain blinding.

Additionally, the unblinded pharmacist or designee will prepare all study drug infusion bags to assure no obvious visual differences between Liquid Alpha₁-PI (Human) and placebo by covering the infusion bag with a non-transparent blinding bag cover.

Furthermore, results of the central laboratory analysis of AAT (activity & antigen) will not be shared with the Investigator, blinded study staff, clinical research organization or blinded Sponsor personnel involved in study conduct.

4.4 Study Treatments

4.4.1 Treatments to Be Administered

- During this clinical trial, subjects randomized to combination Liquid Alpha₁-PI (Human) plus SMT will receive the first dose of blinded Liquid Alpha₁-PI (Human) given as an IV dose of 120 mg/kg (body weight) on Day 1. A second dose of blinded Liquid Alpha₁-PI (Human) (120 mg/kg) will be infused on Day 8 (see Section 6.1). If the subject has been discharged from the hospital at the time of the Day 8 blinded Liquid Alpha₁-PI (Human) infusion, the 2nd infusion is not mandatory, and is at the discretion of the Principal Investigator and subject.

GRIFOLS Bioscience Industrial Group	Number	BIG-CL-PRT-000019
	GC2006 -A Multicenter, Randomized, Open-label, Parallel Group Pilot Study to Evaluate the Safety and Efficacy of Prolastin®-C Liquid plus Standard Medical Treatment (SMT) versus SMT alone in Hospitalized Subjects with	

4.4.1.1 Liquid Alpha₁-PI (Human)

Liquid Alpha₁-PI (Human) has a nominal concentration of Alpha₁-Proteinase Inhibitor of 50 mg/mL. For a subject weighing 75 kg each dose of 120 mg/kg (on Day 1 and Day 8) would require 180 mL of Liquid Alpha₁-PI (Human) to achieve the specified 120 mg/kg dose.

Prior to administration, visually inspect parenteral drug products for particulate matter and discoloration. The product may contain a few protein particles. The solution is clear, colorless or pale yellow or pale green. Do not use if discolored or cloudy. Before delivery to the subject, Liquid Alpha₁-PI (Human) should be brought to room temperature and administered at room temperature for comfort to the subject. Liquid Alpha₁-PI (Human) is for IV administration only. Pooled Liquid Alpha₁-PI (Human) solution should be maintained at room temperature for administration within 3 hours.

Filter the solution during administration using an IV administration set with a suitable 5 to 15-micron infusion filter (not supplied). Infuse Liquid Alpha₁-PI (Human) separately, without mixing with other agents or diluting solutions. Infuse Liquid Alpha₁-PI (Human) IV at 0.08 mL/kg/min as determined by subject response and comfort. The Liquid Alpha₁-PI (Human) infusion line can be flushed with 0.9% sodium chloride for injection. Do Not flush with heparin.

4.4.1.2 Placebo

Sterile 0.9% sodium chloride injection, United States Pharmacopeia (0.9% NaCl, USP) or equivalent will be used as placebo to maintain the blind. The infusion solution will be at a volume commensurate to that required for the appropriate weight-based dose of Liquid Alpha₁-PI (Human) and visually masked to maintain the blind. It will be prepared by the unblinded pharmacist or designee and the infusion bag will be covered with a non-transparent sleeve.

In order to maintain the blind, the placebo infusion will be filtered during administration using an IV administration set with a suitable 5 to 15-micron infusion filter (not supplied).

Sterile 0.9% sodium chloride injection, United States Pharmacopeia (0.9% NaCl, USP) or equivalent will be supplied by the unblinded pharmacist using commercially available saline.

4.4.2 Labeling of Investigational Product

Investigational product will be labeled according to the requirements of local law and legislation.

4.4.3 Packaging of Investigational Product

Packaging and labeling will comply with local regulatory requirements and will be translated into local languages when required per local regulations.

GRIFOLS Bioscience Industrial Group	Number	BIG-CL-PRT-000019	Version	6.0	Status	Effective	Effective Date	08-Dec-2021	Page	41 of 94
	GC2006 -A Multicenter, Randomized, Open-label, Parallel Group Pilot Study to Evaluate the Safety and Efficacy of Prolastin®-CLiquid plus Standard Medical Treatment (SMT) versus SMT alone in Hospitalized Subjects with									

4.4.4 Storage of Investigational product (Liquid Alpha₁-PI (Human))

Store refrigerated at 2-8°C (36-46°F) for the period indicated by the expiration date on its label.

Product may be stored at room temperatures not exceeding 25°C (77°F) for up to one month, after which the product must be used or immediately discarded.

Discard after expiration date. Do not freeze. Discard any unused solution according to local requirements

4.5 Expected Duration of Subject Participation in the Study

The total estimated maximum duration of a subject's participation in terms of actual Clinic Visits will be up to 30 days. Additionally, Phone Checks will occur at Day 60 and Day 90 for vital status (living or deceased), any hospital re-admissions or serious/non-serious adverse events after the Day 29 Final Clinic Visit.

4.6 Discontinuation Criteria for Individual Subjects and Study

4.6.1 Discontinuation Criteria for Individual Subjects

See Section [5.3](#) Subject Withdrawal Criteria

4.6.2 Premature Termination of Study/Closure of Center

The sponsor, Institutional Review Board/Ethics Committee (IRB/EC), and/or regulatory authorities have the right to close this study or a study center, and the investigator/sponsor has the right to close a center, at any time, although this should occur only after consultation between involved parties. The IRB/EC must be informed. Should the study/center be closed prematurely, all study materials (except documentation that has to remain stored at the site) must be returned to the sponsor. The investigator will retain all other documents until notification given by the sponsor for destruction.

The reasons a study center may be closed include, but are not limited to, the following:

- Lack of enrollment
- Non-compliance with the requirements of the study protocol
- Non-compliance with ICH GCP

4.7 Accountability Procedures for Investigational Product

Investigational product is to be used only for the study in accordance with the directions given in this protocol. The investigator, or designee such as the study pharmacist, is responsible for handling of the IP in accordance with directions given in the protocol.

GRIFOLS Bioscience Industrial Group	Number	BIG-CL-PRT-000019	Version	6.0	Status	Effective	Effective Date	08-Dec-2021	Page	42 of 94
	GC2006 -A Multicenter, Randomized, Open-label, Parallel Group Pilot Study to Evaluate the Safety and Efficacy of Prolastin®-CL Liquid plus Standard Medical Treatment (SMT) versus SMT alone in Hospitalized Subjects with									

The investigator is responsible for maintaining accurate records of the IP for his/her site. Investigational product inventory/dispensing documentation verifying the receipt, dispensing, destruction, or return must be maintained and kept current by the investigator, or designee. The inventory must be made available for inspection by the monitor. Investigational product supplies must be accounted for by the monitor and inventory/dispensing logs must be verified by the monitor prior to IP return or destruction. Written documentation of any used and unused inventory is required. At the end of the study, a copy of the inventory/dispensing log(s) will be retrieved by the monitor and returned to Grifols.

4.8 Maintenance of Treatment Randomization Codes

Randomization codes will be generated through an Interactive Response Technology electronic system and access to the actual randomization schedules or codes will be strictly controlled during the course of the study. This study is double-blind so there is blinding of treatment assignment.

4.9 Data to Be Recorded

All information contained in the medical history and complementary exploration reports including laboratory test will be considered as clinical trial source data.

Any data recorded in the Case Report Form should have written or electronic record in the subject's medical records. These written or electronic records will be considered source data and should be dated and signed by the investigator or by the qualified delegated person (eg, results of vital signs testing, or the IP administration procedure).

For every subject enrolled, the investigator will write into his/her medical history that he/she has been enrolled in a clinical trial, specifying its title, study number, and sponsor, as well as the date of ICF provision.

The investigator is responsible for maintaining complete and adequate case histories in source records of each subject. All study-specific data necessary to be recorded in that cannot be found in subjects' past medical records (such as medical history, past medications, etc.) should be recorded by the investigator or their designee in subjects' medical files, dating and signing all new entries.

Source data must be preserved for the maximum period of time as required per local and international regulations and made available by the investigator in the cases described above.

5 SELECTION AND WITHDRAWAL OF SUBJECTS

5.1 Inclusion Criteria

A subject must meet all the following inclusion criteria to be eligible for participation in this study:

GRIFOLS Bioscience Industrial Group	Number	BIG-CL-PPRT-000019	Version	6.0	Status	Effective	Effective Date	08-Dec-2021
	GC2006 -A Multicenter, Randomized, Open-label, Parallel Group Pilot Study to Evaluate the Safety and Efficacy of Prolastin®-CL Liquid plus Standard Medical Treatment (SMT) versus SMT alone in Hospitalized Subjects with COVID-19						Page	43 of 94

1. Hospitalized male or female subject \geq 18 years of age at time of Screening who is being treated for COVID-19. Subjects must be screened within 48 hours (\leq 48 hours) of hospital admission.
2. Has laboratory-confirmed novel coronavirus (SARS-CoV-2) infection as determined by qualitative PCR (reverse transcriptase [RT]-PCR), or other commercial or public health assay approved by regulatory authorities as a diagnostic test for COVID-19 in any specimen during the current hospital admission OR 96 hours prior to the hospital admission date and prior to randomization (the SARS-CoV-2 test results must be performed by a hospital laboratory and the documentation available) .
3. COVID-19 illness (symptoms) of any duration, including **both of** the following:
 - a) Radiographic infiltrates by imaging (chest X-Ray, CT scan, etc.) and/or clinical assessment (evidence of rales/crackles on exam) with SpO₂ $<$ 94% on room air
 - b) **Any One of** the following related to COVID-19: i. Ferritin $>$ 400ng/mL, ii. LDH $>$ 300 U/L, iii. D-Dimers $>$ reference range, or iv. C-reactive protein (CRP) $>$ 40 mg/L
4. Subject provides informed consent prior to initiation of any study procedures.
5. Female subjects of childbearing potential (and males with female partners of childbearing potential) must agree to use of acceptable contraception methods during study (e.g., oral, injectable, or implanted hormonal methods of contraception, placement of an intrauterine device or intrauterine system, condom or occlusive cap with spermicidal foam/gel/film/cream/suppository, male sterilization, or true abstinence*) throughout the study.

*True abstinence: When this is in line with the preferred and usual lifestyle of the subject. (Periodic abstinence [e.g., calendar, ovulation, symptothermal, post-ovulation methods], declaration of abstinence for the duration of a trial, and withdrawal are not acceptable methods of contraception.)

5.2 Exclusion Criteria

A subject meeting any of the following exclusion criteria is NOT eligible for participation in the study.

1. Subjects requiring invasive mechanical ventilation or ICU admission or with PaO₂/FIO₂ \leq 150 mm Hg (i.e., arterial oxygen in mm Hg divided by fraction inspired oxygen concentration [e.g., 0.21 for room air])
2. Clinical evidence of any significant acute or chronic disease that, in the opinion of the investigator, may place the subject at undue medical risk.

GRIFOLS Bioscience Industrial Group	Number	BIG-CL-PRT-000019	Version	6.0	Status	Effective	Effective Date	08-Dec-2021	Page	44 of 94
	GC2006 -A Multicenter, Randomized, Open-label, Parallel Group Pilot Study to Evaluate the Safety and Efficacy of Prolastin®-C Liquid plus Standard Medical Treatment (SMT) versus SMT alone in Hospitalized Subjects with COVID-19									
3. The subject has had a known serious anaphylactic reaction to blood, any blood-derived or plasma product, or known Selective IgA Deficiency with anti-IgA antibodies.										
4. A medical condition in which the infusion of additional fluid is contraindicated (e.g., decompensated congestive heart failure or renal failure with fluid overload). This includes currently uncontrolled congestive heart failure New York Heart Association Class III or IV stage heart failure.										
5. Shock that is unresponsive to fluid challenge and/or multiple vasopressors and accompanied by multiorgan failure considered not able to be reversed by the Principal Investigator										
6. Known alpha-1 antitrypsin deficiency for which the subject is already receiving alpha1-proteinase inhibitor augmentation therapy										
7. Women who are pregnant or breastfeeding. Female subjects of child-bearing potential must have a negative test for pregnancy blood or urine human chorionic gonadotropin (HCG)-based assay at Screening/Baseline Visit.										
8. Subjects for whom there is limitation of therapeutic effort such as “Do not resuscitate” status Note: If the decision is made not to apply treatments or therapeutic procedures that will provide little benefit for the suffering or agony the subject is experiencing, such a subject would not be appropriate for participation in this study and should be excluded.										
9. Currently participating in another interventional clinical trial with investigational medical product or device										
10. Subjects previously requiring long-term oxygen therapy (home oxygen therapy)										
11. History (within the last 2 years) of myocardial infarction, unstable angina, stroke or transient ischemic attacks, pulmonary embolism or deep venous thrombosis										
12. Subject has medical condition (other than COVID-19) that is projected to limit lifespan to ≤ 1 year										
13. Systolic blood pressure < 100 mm Hg or > 160 mm Hg (uncontrolled hypertension) at the time of Screening										
14. Alanine aminotransferase (ALT) ≥ 2 times the upper limit of normal (ULN)										
15. Any elevation of total bilirubin at the time of Screening										
16. Estimated glomerular filtration rate (eGFR) < 45 mL/min (or subject is dependent on dialysis/renal replacement therapy) at the time of Screening										
eGFR is calculated by the Cockcroft-Gault equation: For men:										

GRIFOLS Bioscience Industrial Group	Number	BIG-CL-PRT-000019	Version	6.0	Status	Effective	Effective Date	08-Dec-2021
	GC2006-A Multicenter, Randomized, Open-label, Parallel Group Pilot Study to Evaluate the Safety and Efficacy of Prolastin®-C Liquid plus Standard Medical Treatment (SMT) versus SMT alone in Hospitalized Subjects with						Page	45 of 94

$$\frac{(140 - \text{age in years})(\text{body weight [kg]})}{(72)(\text{serum creatinine } \frac{\text{mg}}{\text{dL}})}$$

For women:

$$\frac{0.85 \times (140 - \text{age in years})(\text{body weight [kg]})}{(72)(\text{serum creatinine } \frac{\text{mg}}{\text{dL}})}$$

17. Hemoglobin < 10 g/dL at the time of Screening
18. Absolute neutrophil count < 1000/mm³ at the time of Screening
19. Platelet count < 75,000/mm³ at the time of Screening
20. Subject has history of drug or alcohol abuse within the past 24 months
21. Subject is unwilling to commit to follow-up visits
22. Known history of prothrombin gene mutation 20210, homozygous Factor V Leiden mutations, antithrombin III deficiency, protein C deficiency, protein S deficiency or antiphospholipid syndrome

5.3 Subject Withdrawal Criteria

Subjects have the right to withdraw from the study at any time for any reason, either before or after the infusion of the IP. The investigator can withdraw a subject from the clinical trial at any time.

The investigator will document the reason(s) for withdrawal of each subject in source documents and study record. All data gathered on the subject prior to termination will be made available to the sponsor.

5.3.1 Screen Failures

Screening evaluations will be used to determine the eligibility of each subject for enrollment. Subjects who fail to meet eligibility criteria during screening evaluations will be considered screen failures and will not participate in the study. Outcomes of screening evaluations will be documented in subject's source documents (e.g. medical history) - including compliance with each individual inclusion/exclusion criterion- and in study records as well.

5.3.2 Removal of Subjects

Subjects may withdraw or be withdrawn from the study for the following reasons:

1. At their own request or at the request of their legally acceptable representative.
2. If, in the investigator's opinion, continuation in the study would be detrimental to the subject's well-being.
3. At the specific request of the sponsor.

GRIFOLS Bioscience Industrial Group	Number	BIG-CL-PRT-000019	Version	6.0	Status	Effective	Effective Date	08-Dec-2021	Page	46 of 94
	GC2006 -A Multicenter, Randomized, Open-label, Parallel Group Pilot Study to Evaluate the Safety and Efficacy of Prolastin®-C Liquid plus Standard Medical Treatment (SMT) versus SMT alone in Hospitalized Subjects with									

Also, subjects may be withdrawn for the following reasons:

1. The subject is not able to adhere to the main protocol requirements (major protocol violations).
2. The occurrence of an AE which in the investigator's opinion requires the withdrawal of the subject from the clinical trial.
3. The occurrence of pulmonary embolism whether or not related to COVID-19
4. The subject is lost to follow-up.
5. Subject's death.
6. Any event which in the opinion of the investigator impedes the subject's participation in the study.

In all cases, the reason for withdrawal must be recorded in the study record and in the subject's records.

5.3.3 Subject Replacement

Subjects who are withdrawn from the study after being randomized will not be replaced.

5.3.4 Follow-up of Subjects Withdrawn from Study

For subjects administered any amount of blinded Liquid Alpha₁-PI (Human) or blinded placebo who withdraw from the clinical trial prior to Day 29, study procedures and assessments scheduled for the Day 15 Visit will be performed at the time of withdrawal, during an unscheduled visit. In addition, to assure major clinical outcomes are adequately captured as a measure of overall safety, these subjects will be asked to return for their chronological Day 29 Clinic Visit (ie, 28 days after Day 1 baseline), provided that they or their legally acceptable representative have not withdrawn consent. At the chronological Day 29 Clinic Visit, all assessments will be performed *except for* central laboratory testing: cytokine panel, levels of alpha 1-PI (AAT) activity and antigen, respiratory sample for quantitative measurement of SARS-CoV-2 viral load (obtained via nasopharyngeal swab), and quantitative measurement of IgM and IgG antibodies, *which are not required for these subjects at chronological Day 29 for premature withdrawals*. Note: A Day 29 Clinic Visit would not be necessary if the unscheduled visit is within 4 days of the subject's chronological Day 29 visit because the assessments/outcome measures would be the same and would not need to be repeated in such a short a time interval.

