- Hematology: absolute neutrophil & lymphocyte count and standard hematology (hemoglobin, hematocrit, platelet count, leukocyte count with differential)
- Assessment of ARDS (Berlin Criteria) ([Appendix 3](#))
- Ferritin (serum), D-dimer (plasma, sodium citrate tube), CRP (serum)
- Cytokine panel (IL-1 β , IL-10, IL-6, IL-8, IL-2, interferon γ , and TNF- α). Note: serum samples must be stored at -70° C for later analysis at a reference laboratory.
- Levels of alpha 1-PI (AAT) activity and antigen; both plasma (sodium citrate) and serum samples to be stored at - 70° C for measurement of both antigenic content and functional activity (potency).
- Record SAEs and TEAEs
- Record standard care concomitant medications

After all Screen/Baseline assessments are complete subjects may be randomized.

Subjects may receive the first infusion of blinded Liquid Alpha₁-PI (Human) or Placebo on Screen/Baseline and Randomized Treatment visit (Day 1) if eligibility criteria are met, and all pre-infusion assessments are performed. The intent is for infusion of blinded Liquid Alpha₁-PI (Human) or Placebo to commence as rapidly as feasible on Day 1. If there is unanticipated delay due to pandemic conditions, while not ideal, proceed with the first blinded Liquid Alpha₁-PI (Human) or Placebo infusion as rapidly as possible.

During study infusion vital signs will be measured immediately before the start of infusion, after the first 5 minutes of infusion, and subsequently at 5-10-minute intervals during infusion until the end of infusion. Vital signs will also be measured 2 hours after the end of study infusion.

Record all infusion details and date/time in the CRF on the specific “1st IP infusion day” page and continue with all protocol-specified assessments.

All Study Days are relative to Day 1 (Screen/Baseline and Randomized Treatment visit).

7.2.3 SMT and Daily Evaluations (Days 2 through 10 if still hospitalized) and Mandatory Day 5 Assessments for All Subjects

All subjects receive continued SMT. **On Day 8 all subjects will receive a second double-blind infusion of blinded Liquid Alpha₁-PI (Human) or Placebo. Subjects randomized to Liquid Alpha₁-PI (Human) will receive a second blinded dose of 120 mg/kg body weight. Subjects randomized to Placebo will receive a second blinded infusion of sterile 0.9%**

GRIFOLS Bioscience Industrial Group	Number	BIG-CL-PRT-000019	Version	6.0	Status	Effective	Effective Date	08-Dec-2021

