9 STATISTICS

9.1 Statistical Methods

Descriptive statistics will include the number of non-missing observations, mean, standard deviation (SD), median, minimum, and maximum values for the continuous/quantitative data or absolute and relative frequency counts and percentages for categorical/qualitative data. All statistical tests will be 2-sided at a significance level of 0.05.

An interim analysis will be conducted after 50 subjects (approximately 25 per group) for safety variables through Day 29. Due to the exploratory nature of this phase 2 study, the multiplicity adjustments will not be considered; full details will be described in the statistical analysis plan.

Interim Futility Analysis: An interim futility analysis will be conducted to assess whether the trial will be terminated due to lack of efficacy (futility) based on all available data assessable for the primary endpoint and key secondary efficacy endpoints.

There will be 3 analysis populations in this study; 2 populations for efficacy assessments and 1 population for safety evaluation.

The intention to treat (ITT) population is defined as all subjects who are randomized. The ITT population will be used for all efficacy analyses.

The Per-Protocol (PP) population is defined as the subset of subjects included in the ITT population who do not present major protocol violations which might have an impact on the

GRIFOLS Bioscience Industrial Group	Number	BIG-CL-PRT-000019	Version	6.0	Status	Effective	Effective Date	08-Dec-2021	Page	66 of 94
	GC2006 -A Multicenter, Randomized, Open-label, Parallel Group Pilot Study to Evaluate the Safety and Efficacy of Prolastin®-CL Liquid plus Standard Medical Treatment (SMT) versus SMT alone in Hospitalized Subjects with COVID-19									

primary efficacy endpoint, and complete at least 80% of the IP. The primary efficacy analyses will be carried out using the PP population if different from the ITT population.

The Safety population is defined as the subset of subjects who receive at least any amount of Liquid Alpha₁-PI (Human) plus SMT or placebo plus SMT. Safety analyses will be based on the Safety population.

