The primary efficacy analysis will be carried out on the ITT population and repeated on the PP population (if different from the ITT population) by Fisher's exact test. Secondary and exploratory efficacy analyses will be analyzed by means of Kaplan-Meier survival estimates and curves and compared between treatment groups by means of the Log-rank test for time to event variables, analysis of covariance (ANCOVA) when adjusting for covariates, or analysis of variance (ANOVA) when without covariates for normally-distributed variables or Wilcoxon rank-sum test for non-normally-distributed variables. Detailed data handling and evaluation procedures and details of the interim review will be described in the Statistical Analysis Plan (SAP).

For the primary endpoint, if the value of the subject is missing, then a conservative imputation rule will be used such that the subject will be treated as having met the condition for the primary efficacy analysis. The choice of analysis method for primary, secondary and exploratory efficacy endpoints will be described in detail in the SAP which will be finalized and signed off before data analysis is performed.

The SAP may include exploratory analyses of various aspects of SMT inclusive of different interventional strategies and evolving treatment modalities. Grifols will analyze the use of COVID-19 specific, potentially disease modifying treatments for any potential differences between study arms. This analysis will be fully detailed in the SAP since medical understanding of COVID-19 interventions is rapidly evolving. For ethical reasons, there are no restrictions placed on what are perceived to be potentially life-saving therapies (apart from participation in another interventional clinical trial).

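### Protocol 5.3.4 requires a Day 29 check after withdrawal only for dosed subjects, so a randomised subject who withdraws before the infusion is scored as a primary-endpoint event by default

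*Protocol*

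**What the plan says.** Protocol 5.3.4 is the only rule on follow-up after withdrawal, and the schedule in Appendix 1 refers early withdrawals to it. It opens "For subjects administered any amount of blinded Liquid" Alpha1-PI (Human) or placebo. It then says that "these subjects will be asked to return for their chronological Day 29 Clinic Visit", provided consent has not been withdrawn. The stated purpose is "to assure major clinical outcomes are adequately captured as a measure of overall safety".

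Protocol 5.3 allows withdrawal before as well as after the infusion. Under 5.3.3, "Subjects who are withdrawn from the study after being randomized will not be replaced".

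Protocol 9.1 states that "The intention to treat (ITT) population is defined as all subjects who are randomized", and both protocol 9.1 and SAP 6.1 place the primary analysis on that population. For the primary endpoint, protocol 9.1 says that "if the value of the subject is missing, then a conservative imputation rule will be used", meaning that the subject is counted as having had the event. SAP 6.1 is stricter in detail. If any one of its four criteria cannot be assessed because data are missing, the subject is an event. The ventilator and high-flow oxygen criteria are read from the Day 29 eCRF page.

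**The concern.** The collection rule in 5.3.4 is built around exposure, as suits a safety purpose. The primary analysis is built around randomisation. Between the two lies the subject who is randomised, not dosed and withdrawn. Nothing requires the site to find out that subject's Day 29 status, although it may need only a phone call or a look at the hospital record. Without a Day 29 page, SAP 6.1 scores the subject as an event whatever actually happened.

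Some of the primary events could therefore be produced by the follow-up rule and not by the disease. If the arms are equally affected, the cost is sensitivity. If they are not, the treatment comparison is biased. At about 50 per arm, one imputed event is 1/50 = 2 percentage points of an arm's proportion.

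**Working it through.** The documents state no event rate, effect size, power or dropout, so there is no planned figure to reproduce. The check has two parts.

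**1. The chain of rules**

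- Post-withdrawal and Day 29 visits: dosed subjects only (protocol 5.3.4).
- Withdrawal before infusion: possible (protocol 5.3), with no replacement (5.3.3).
- Primary population: all randomised subjects (protocol 9.1, SAP 4.2 and 6.1).
- Missing primary endpoint: event (protocol 9.1, SAP 6.1), with two of the four criteria taken from the Day 29 page.
- Other contacts: the Day 60 and Day 90 phone checks (protocol 7.2.8) ask for vital status, re-admissions and adverse events. They do not ask for ICU admission or for oxygen or ventilator status on Day 29, so they cannot complete the endpoint.

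The chain closes. A subject with a recorded death or ICU admission is an event anyway, so only those who would have been event-free are misclassified.

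**2. Size, under assumptions**

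Inputs from the documents: 1:1 allocation, about 100 subjects (n = 50 per arm), two-sided 0.05, chi-square test (SAP 6.1, taken here without continuity correction). Assumed: true event rates pC on placebo and pT on active, and k undosed withdrawals per arm. Power is by exact enumeration of all 2×2 tables.

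*Balanced case, pC = 30%, pT = 10%.* The right comparator is what would be seen if the same subjects were followed. An undosed active-arm subject receives no drug, so the placebo rate is assumed for that subject.

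- Imputed rates: (p(n − k) + k)/n. For k = 2, active (0.10 × 48 + 2)/50 = 13.6% and placebo (0.30 × 48 + 2)/50 = 32.8%, a difference of 19.2 points.
- Observed rates: for k = 2, active (0.10 × 48 + 0.30 × 2)/50 = 10.8% and placebo 30.0%, also a difference of 19.2 points.

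| k per arm | Power, imputed | Power, observed | Cost of the rule |
|---|---|---|---|
| 0 | 73.4% | 73.4% | 0 |
| 1 | 69.2% | 71.2% | 2.0 points |
| 2 | 65.0% | 68.9% | 3.9 points |

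In this case the drop in the risk difference from 20.0 to 19.2 points comes from non-dosing, and follow-up would not recover it. What imputation adds is a higher event rate in both arms. That dilutes the relative effect (13.6/32.8 = 0.41 against 10.8/30.0 = 0.36) and increases the variance, which is where the extra power goes.

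*Unbalanced case, pC = pT = 20%, k = 3 in one arm only.* Shift in the difference = k(1 − p)/n = 3 × 0.80/50 = 4.8 points against the arm with the withdrawals. The two-sided rejection rate under no effect rises from 5.2% to 7.8%.

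*A single event near the boundary.* 6/50 versus 15/50 gives p = 0.027. One imputed event added to the smaller count, 7/50 versus 15/50, gives p = 0.053.

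**The case against.** The strongest reply is that the gap is narrow. Section 5.3.4 concerns subjects who withdraw. A subject who misses the infusion but stays in the study remains under protocol 7.2.7, which is headed for all subjects, and Appendix 1 makes Day 29 mandatory even after discharge. This stands. A reader might infer that every undosed subject lacks follow-up, or that Day 29 data may not be collected from undosed withdrawals. The documents support neither: nothing is required for that subset, and nothing is forbidden.

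The window is also short. Randomisation follows the baseline assessments and infusion is intended on Day 1. The delay sentence in 7.2.2, "If there is unanticipated delay due to pandemic conditions, while not ideal, proceed with the first blinded" infusion as fast as possible, foresees late dosing and not missed dosing.

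A reader might suspect that non-dosing falls mainly on the active arm, because placebo "will be supplied by the unblinded pharmacist using commercially available saline" while active drug needs sponsor vials. No supply failure is documented, the documents do not say whether the randomisation system checks stock, and 4.4.4 lets the product be kept at room temperature for up to a month. Only the pharmacist or designee at the site knows the assignment (4.3.3), so withdrawal decisions should be balanced. The unbalanced case is a sensitivity illustration, not a prediction.

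Finally, the primary analysis is repeated in the per-protocol population, which requires at least 80% of the product and so excludes undosed subjects. A discrepancy might show there. That population is not the randomised set, however, so it does not repair the primary result. The SAP plans no sensitivity analysis of the missing-equals-event rule itself.

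**Conclusion.** The mismatch is real and follows from the current text of both documents. It concerns only subjects who are randomised, undosed and withdrawn. Their number is probably small and balanced, so the likely effect is a modest loss of sensitivity: about 2 power points with one per arm and about 4 with two, under the assumed 30% versus 10%. Bias arises only if the arms differ.

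Two stronger readings should not be drawn. First, the fall from 73.4% to 65.0% with two per arm is not all due to the rule, since observing the same subjects would give 68.9%. Second, it is not established that imputed subjects enter the futility conditional power. SAP 8.2 limits the primary endpoint there to patients with data through Day 29, which would leave them out, yet it also points to the methods of 6.1, which would impute them. The text is ambiguous.

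This is a cheap improvement to an exploratory phase 2 plan. It does not invalidate the analysis.

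**What to change.** Reword the opening condition of protocol 5.3.4 so that the Day 29 outcome check applies to all randomised subjects who withdraw, and not only to those given some study drug or placebo. For undosed subjects, require at least:

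- vital status at Day 29;
- any ICU admission through Day 29;
- high-flow oxygen and ventilator status on Day 29.

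Allow these to come from a visit, a phone call or the hospital record, unless consent to follow-up is withdrawn. Count Day 29 from randomisation for these subjects, because SAP 4.6 counts study days from first drug administration and gives them no Day 29.

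In protocol 9.1 and SAP 6.1, apply the missing-equals-event rule only when this information cannot be obtained. In SAP 8.2, state whether imputed subjects enter the conditional power.

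The cost is a few sentences and a call or chart check for a few subjects. Those who refuse follow-up would still be imputed, so the change reduces the problem without removing it.
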